### 1.3. System components

- Urine receptacle

The urine receptacle is comprised of a plastic cup which holds the subject's urine. It is designed to hold a sufficient amount of urine and allow for easy immersion of the test strip.

***Image 1:*** Closed Plastic Cup

- ACR urine test strip

A single-wrapped ACR urine reagent strip (microalbumin/creatinine). The strip consists of 3 chemical reagents, which change color after being immersed in a urine sample. One patch for albumin, another for creatinine and an additional compensation patch.

***Figure 2:*** Urine Test Strip

- Absorbing pad

A single piece of standard absorbing material. It is designated to assist in absorbing remaining liquids from the strip after it has been immersed in the urine sample.

- Color-Board

A cardboard-based, high-quality printed Color-Board facilitates the image recognition process. Its main functions are:

- Proper positioning of the urine strip in the frame.
- Neutralization of the surrounding lighting and/or camera interruptions.
- Providing a reference color spectrum for the strip reagent colors based on a data algorithm.

**Figure 3:** Color-Board

- Smartphone app

The smartphone application (supported by the iPhone 11 device running iOS 13 and Google Pixel 3a running OS 10) is designed to enable the following:

- Device interface instructions for the user to ensure proper performance of the urinalysis test, avoiding key human errors. These include interactive video texts and sound instruction to guide the users through the testing procedure.
- The software includes an augmented reality layer on the smartphone camera which guides users while taking the scan. This is a real-time analysis of the scan, which finds and centers the Color-Board within the camera frame. The software will also analyze the scan and evaluate if it meets the system boundary conditions for urinalysis measurement. If not, the software will instruct the user to take another scan which can be analyzed.
- Presentation of urinalysis measurement result to a clinician for viewing and interpretation.

[figure not shown]
- Software

The ACR | U.S. smartphone algorithm is a cloud-based, image-processing system. Both albumin and creatinine analytes are analyzed based on a separate, unique set of eight target colors and a set of calculations which are completely independent from each other. Once these two measurements are taken, the algorithm on the cloud will use these two numbers to calculate the subsequent Albumin-Creatinine Ratio, which is measured in units of mg/g or mg/mmol.

#### **1.4. Intended Use**

The ACR | U.S. Urine Analysis Test System is an in-vitro diagnostic, home-use device for the semi-quantitative measurement of the Albumin-Creatinine Ratio (ACR). The device consists of a smartphone application, proprietary Color-Board and an ACR reagent strip. The device is available for prescription-use only. Results are intended to be used in conjunction with clinical evaluation as an aid in the assessment of kidney function.

**Figure 4: Smartphone Application Screens**

## 2. PERFORMANCE TESTING AND CLINICAL EVALUATION

---

### 2.1. ACR | U.S. Performance Tests

Healthy.io has designed a series of bench-testing experiments to verify the performances of the ACR | U.S. These tests have been designed according to the guidance provided by the Clinical and Laboratory Standards Institute (CLSI).

- **Precision:** Comprises two separate tests - Repeatability and Reproducibility. The precision studies are designed in accordance with guidance provided by Clinical and Laboratory Standards Institute document *EP05-A3 – Evaluation of Precision of Quantitative Measurement Procedures; Approved Guideline – Third Edition*.
  - Repeatability is defined as the closeness of the agreement between results of successive measurements of the same measure and carried out under the same conditions of measurement.
  - Reproducibility is defined as closeness of the agreement between the results of measurements of the same measure carried out under changed conditions of measurement over the course of multiple days.
- **Interference:** Testing of potential interfering substances with the ACR | U.S. was designed in accordance with guidance provided by the Clinical and Laboratory Standards Institute document *EP07 – Interference Testing in Clinical Chemistry; Approved Guideline – Third Edition*.
- **Limit of Detection:** Testing of the ACR | U.S. assay's detection was designed in accordance with guidance provided by Clinical and Laboratory Standards Institute (CLSI) document *EP17-A2 – Evaluation of Detection Capability for Clinical Laboratory Measurement Procedures; Approved Guideline – Second Edition*.
- **Linearity:** Testing the linearity of the ACR | U.S. was designed in accordance with guidance provided by the Clinical and Laboratory Standards Institute (CLSI) document *EP06-A – Evaluation of Linearity of Quantitative Measurement Procedures: A Statistical Approach; Approved Guideline*
- **Stability:** The stability experiment is designed to evaluate the environmental conditions under which the ACR | U.S. is suitable for its intended use. This study was designed with the guidance provided by the Clinical and Laboratory Standards Institute (CLSI) document *EP-25A Evaluation of In-Vitro Diagnostics Reagents; Approved Guideline*.
- **Additional Studies-**

- **Illumination Study:** Healthy.io designed an experiment to test the ACR | U.S. under multiple lighting conditions.
- **Boundary Study:** Healthy.io designed an experiment to test the physical boundaries (such as the phone's distance and angle in relation to the Color-Board) which would prevent the ACR | U.S. from capturing an accurate image that can be evaluated by the algorithm.
- **Multiple Phones and Operating Systems Study:** Healthy.io designed an experiment to test the ACR | U.S. with multiple smartphone devices and operating systems versions (iOS and Android).
- **Timing Flex Study:** Healthy.io designed an experiment to test the impact of different dipping times, assay-times, and strip wetting times on the ACR | U.S.

## 2.2. Albumin-Creatinine Ratio Urinalysis Method Comparison Studies:

The following table (*Table 1.0*) summarizes the method comparison studies conducted on several marketed lab urine analyzers and test strips with similar indications for use as the ACR | U.S.

The key difference being that these studies were operated by lab professionals while the ACR | U.S. is intended for lay users who are operating the device at home.

**Table 1.0:** Urinalysis analyzers method comparison studies summary:

Study details	Mission U120 Ultra Urine (K142391) 	Uritek TC-201 Urine Analyzer (K152835) 	URiSCAN Optima Urine Analyzer (K141874) 
No. of urine samples	429 samples	402	351
Urine sources	Fresh	Fresh	Fresh

 See the 510(k) Substantial Equivalence Determination Decision Summary:  
[https://www.accessdata.fda.gov/cdrh\\_docs/reviews/K142391.pdf](https://www.accessdata.fda.gov/cdrh_docs/reviews/K142391.pdf)

 See the 510(k) Substantial Equivalence Determination Decision Summary:  
[https://www.accessdata.fda.gov/cdrh\\_docs/reviews/K152835.pdf](https://www.accessdata.fda.gov/cdrh_docs/reviews/K152835.pdf)

 See the 510(k) Substantial Equivalence Determination Decision Summary:  
[https://www.accessdata.fda.gov/cdrh\\_docs/reviews/K141874.pdf](https://www.accessdata.fda.gov/cdrh_docs/reviews/K141874.pdf)

Study details	Mission U120 Ultra Urine (K142391) 	Uritek TC-201 Urine Analyzer (K152835) 	URiSCAN Optima Urine Analyzer (K141874) 
Percentage of Contrived Samples Used	12-13%	9%	0%
Subjects medical history	
From 510k summary:
 
"Test results may be used in screening urine specimens for microalbuminuria as an aid in the detection of patients at risk for developing kidney damage."
 
From User Manual:
 
"Patients with the highest risk of developing early kidney damage are those with diabetes and hypertension, followed by patients who have immune disorders or have been exposed to nephrotoxins."
	
From the 510K summary:
 
"Test results may be used in screening urine specimens for microalbuminuria as an aid in the detection of patients at risk for developing kidney damage."
	
From the 510K summary:
 
"These measurements are useful in the evaluation of renal, urinary and metabolic disorders."

Compared predicate	Clinitek Status Analyzer (K031947)	Clinitek Status+ Analyzer (K091216)	Clinitek Status (Siemens) (K091216)
No. of strip lots	3	3	3

### **3. RATIONALE FOR THE STUDY**

---

In addition to the analytical performance tests described above, method comparison and usability tests are crucial steps before companies are permitted to bring such a device to market. All marketed urinalysis devices and urine test strips for home use have performed method comparison and usability studies tested by the intended lay user. Normally in these studies, urine samples are collected and tested by a lay user, using the new home use device, and by a device operator or lab professional using the comparison device. The lay user test results are compared to the results obtained by testing the same urine sample on the comparison device. The method comparison and usability studies provide data on the accuracy and usability of the device, including the lay user's ability to understand and implement the user manual instructions and evaluate the ease of use of the device under actual use conditions (home environment). Moreover, the study provides valuable data originating from unhealthy subjects using mostly their real urine samples and can strengthen the results of the bench analytical tests. The urine samples should be sourced from pathological subjects simulating the "realistic clinical environment" or from healthy subjects, spiked samples to cover the entire color range of the analyte detection reagents.

The ACR | U.S. method comparison study should include similar elements and be designed similarly to previously tested urinalysis analyzers. The study design is meant to demonstrate that the ACR | U.S. may be easily used by a lay person and the results are in agreement with another legally marketed urine analyzer device.

### **4. OBJECTIVES**

---

The aim of the study is to evaluate the accuracy and usability performance of ACR | U.S. in the hands of the potential lay user.

#### **4.1. Primary Objective**

The primary objective of the study is to evaluate the % exact match (agreement) and the %  $\pm 1$  block match (agreement) of ACR | U.S. (tested by the lay user) compared to the URiSCAN Optima Urine Analyzer (the comparator device, tested by a healthcare professional), for each tested concentration (block).

#### **4.2. Secondary Objective**

The secondary objective of the study is to evaluate the ACR | U.S. usability, by potential lay users under actual use conditions (home environment).

### **5. STUDY POPULATION**

---

#### **5.1. General Considerations**

The study will recruit at least 250 subjects from multiple sites, including patients with a disease that normally represents itself with an abnormal concentration of albumin. Examples of such diseases include Diabetes Type I/Type II, Hypertension, any kidney disease etc., or healthy patients. All genders, all ethnicities, and subjects between 18-80 years of age will be recruited for the study. Subjects will be recruited from the study sites, and if appropriate, from the study center's database. Informed consent will be obtained from potential subjects according to local and national IRB requirements. Potential candidates will be screened according to the following inclusion/exclusion criteria.

#### **5.2. Inclusion Criteria**

- Males and Females 18-80 years of age.
- Subjects diagnosed with a disease that normally represents itself with an abnormal concentration of albumin:
  - Diabetes Type I/Type II,
  - Hypertension,
  - any kidney disease,
  - other relevant conditions,
- or, subjects who are healthy or pregnant.
- Subject is familiar with the use of a smartphone.
- Subject is capable of comprehending and following instructions in English.
- Subject has facility with both hands.
- Subject is capable and willing to adhere to the study procedures.
- Subject is capable and willing to provide informed consent.

### **5.3. Exclusion criteria**

- Subject has dementia.
- Subject has severe mental disorders.
- Subject cannot collect urine in a receptacle.
- Subject is visually impaired (cannot read the user manual).
- Any additional reason the study physician believes disqualifies the subject from participating in the study.

## **6. STUDY DESIGN**

---

The Method Comparison Test is a clinical study using actual human urine samples that will be collected in a lab-based hospital setting. These include urine samples from diseased subjects (e.g. patients with Type 1 and Type 2 Diabetes and Hypertension), as well as from patients who are undergoing routine physical examinations.

### **6.1. Framework:**

- At least 250 patients will be recruited to participate
- Up to 15% of the samples may be spiked urine samples in case of insufficient native samples in certain blocks
- Multiple sites
- 2 mobile phones: iPhone 11 and Google Pixel 3a (per subject)
- 3 strip lots which will be used interchangeably throughout the experiment

**6.2. Population:** The study is a comparative, controlled trial of subjects who will be recruited from a research clinic. The study population will consist of patients with a medical history of diabetes Type I, Type II, Hypertension, kidney disease and other ailments that represent the target population for urine testing or healthy patients. The intention is to recruit subjects with ailments that will cover all test analytes and all concentrations of these analytes. In the case that analytes and concentrations will not be covered by enrolled subjects, the study will be supplemented with spiked urine samples with the missing analytes and concentrations. However, the number of spiked samples will not exceed 15% of the total samples (all bins combined). Lay users will test their own urine with both smartphones and additionally

may be asked to test another spiked sample, that will be provided by the study staff as necessary and in accordance to protocol.

**6.3. Testing Methods:** Subjects will be recruited for the clinical trials based on their ability to provide a urine sample and comfortably complete tasks using a smartphone. Each urine sample should be tested by a lay user on the ACR | U.S. app, and then transferred to a professional user to conduct the test on the Optima device. The professional user will be blinded to the results of the lay user until after they have completed the test using the Optima device.

**6.4. Timing:** Collection of a urine sample is performed by the patient as part of the study flow. Within 15 minutes from the time of patient's test, testing on the comparator analyzer should be done. This is to best simulate the real-case usage of the ACR | U.S. test. The specimen should not be centrifuged or refrigerated in between tests.

**6.5. Analyzers:** Each urine sample will be tested using the iPhone 11 and Google Pixel 3a devices running the ACR | U.S. application. Each test will be compared to the URiSCAN Optima Analyzer, the comparator device.

**6.6. Reagent Strips:** To control for bias among the test strips, three lots of reagent strips will be used during the study. To enable an equal and unbiased distribution of the lots, one lot will be randomly selected by the professional user for the testing of each sample. Separate strips will be used in each test: with the ACR | U.S. and the Optima analyzer.

**6.7. Requirements:** The Method Comparison Study must be conducted in accordance with Good Clinical Practice (GCP), according to 21 CFR Part 50, 54, 56, 812, ISO14155-1/2 and relevant local and national regulations (IRB or Helsinki EC approved). The Method Comparison Study shall comply with *CLSI EP09c: Method Comparison and Bias Estimation Using Patient Samples; Approved Guidelines – Third Edition*. Since the ACR | U.S. is classified as a urinalysis analyzer intended for lay users to test their urine in a home environment, the design of the device clinical comparative study should include parameters from both lab urinalysis analyzers and urine strip method comparison studies. The study design is mainly based on the above-mentioned method comparison studies in section 3.2 when used by a lay user and FDA recognized consensus standards CLSI EP09c and for usability testing of medical devices - *ANSI/AAMI/IEC 62366-1:2015 Medical devices – Part 1: Application of usability engineering to medical devices*.

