  - 2) The subject will be placed in the private room, with restroom accessibility and internet connectivity, to perform the urinalysis test and complete the task list found below. No training, assistance, feedback, or supplemental instructional materials, other than those described, will be provided to participants. The healthcare professional or other site staff will not be allowed to intervene or answer questions from the subjects during testing, although a 1-800 or clinical assistance phone number, which will be provided to the subject in actual use, will be made available to the subject in case contact is attempted by the subject.
  - 3) The room will be prepared with a desk and chair. The ACR | U.S., in its original packaging will be placed on the desk. The device packaging contains the kit components and the user manual. An in-app instructional guide containing the information most critical to safety and effectiveness is also provided in the form of a readable and understandable, visual, and textual guide on the device App. The patient labeling will be in the format intended for distribution to allow for a realistic evaluation of the labeling effectiveness.
  - 4) The subjects will be asked to follow the device user manual and/or the in-app instructional guide and perform the following tasks:
    - Access the ACR | U.S. App on the smartphone. (iPhone 11 or the Google Pixel 3a)
    - Provide a urine sample in the urine receptacle (to the level marked on the cup) that is included in the ACR | U.S. kit.
    - Immerse the urine strip (provided in the ACR | U.S. kit) in the collected urine specimen for one second.
    - Place the urine strip on the designated area on the Color-Board and wait at least 75 seconds, but not more than 180 seconds.
    - Scan the urine strip and Color-Board with the smartphone App.
    - Send the test results to the study clinician using the smartphone App.
    - Subjects will be asked to complete a questionnaire following completion of the tasks.

[figure not shown]
- 5) Subjects will be observed as they complete the tasks by a research staff member. The research staff observer will complete a dedicated post-test questionnaire.

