### **9.2. Withdrawal from the study**

A subject will be withdrawn from the study for any of the following reasons:

1. Patient has identified that he/she cannot provide a sufficient urine sample.
2. Withdrawal of consent.
3. Patient is not compliant with requirements of the study, including inclusion and exclusion criteria.
4. The study is prematurely stopped or halted (e.g. clinical halt).
5. The investigator believes that for safety reasons (e.g. an adverse event) it is in the best interest of the patient to stop the test.

When a patient withdraws before completing the study, the reason for withdrawal will be documented in the CRF.

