## **10.6. Statistical Analysis**

- General Considerations

Statistical analyses will be performed using an appropriate statistical program and methodology.

Baseline demographic and safety analyses will be performed on all enrolled subjects.

- Demographic and Other Baseline Variables

Demographic and baseline condition related characteristics will be tabulated. Continuous variables will be summarized by a mean, standard deviation, minimum, median and maximum, and categorical variables by a count and percentage.

- Disposition of Subjects

The number and percent of subjects who fail to complete the study and the number and percent of subjects who fail to complete the study because of Adverse Events will be presented.

- Efficacy Analysis

The % exact match (agreement) of the ACR | U.S. compared to the comparator device, for the same Albumin-Creatinine Ratio concentration (block) will be calculated. The %  $\pm 1$  block match (agreement) of the ACR | U.S. compared to the comparator device, for the same Albumin-Creatinine Ratio concentration (block) will also be calculated.

- Usability Analysis

The usability of the ACR | U.S. will be determined by evaluating the percentage of study subjects who are able to complete the device-related tasks, including accessing the ACR | U.S. App, providing a urine sample in the urine receptacle, dipping the kit urine strip in the urine specimen, positioning the strip on

the Color-Board and taking a picture using the smartphone App, with minimal attempts to ask for assistance.

Measurable usability criteria for specific, critical steps, such as time-to-completion, number of requests for assistance, numerical ratings, etc., will be evaluated by observer evaluation and user questionnaire responses. Descriptive statistics will be provided for usability criteria.

- Adverse Event

In general, there are no anticipated adverse events in this study; however, if any adverse events do occur they will be recorded and presented in tables.

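### Section 6.3 sets a stricter smartphone entry rule than 5.2, and 10.5 and 9.2 leave the usability denominator open, so the usability percentage may be biased upward by an unknown amount, possibly zero

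*Combined protocol and SAP*

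**What the plan says.** - **Entry.** Section 6.3 (Testing Methods) gives this basis for recruitment: "Subjects will be recruited for the clinical trials based on their ability to provide a urine sample and comfortably complete tasks using a smartphone". The matching inclusion criterion in 5.2 is "Subject is familiar with the use of a smartphone". Section 5.3 excludes a person for whom "Subject cannot collect urine in a receptacle" applies.
- **Endpoint.** Under Usability Analysis, 10.6 takes the "percentage of study subjects who are able to complete the device-related tasks". The named tasks are opening the app, "providing a urine sample in the urine receptacle, dipping the kit urine strip in the urine specimen", placing the strip on the Color-Board and taking the picture. The task list in 7.1 (Stage V) includes "Provide a urine sample in the urine receptacle (to the level marked on the cup".
- **Pass rule.** Section 9.1 scores a subject as passing on a successful scan of the Color-Board.
- **Withdrawal.** Section 9.2 lists as reasons "Patient has identified that he/she cannot provide a sufficient urine sample" (item 1) and "Patient is not compliant with requirements of the study, including inclusion and exclusion criteria" (item 3). The reason is recorded in the CRF.
- **Analysis set.** Section 10.5 uses the efficacy set for usability. That set is limited to subjects with no major protocol deviation, and the definitions of minor and major are left for later. Section 10.6 tabulates non-completers under disposition.

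**The concern.** The secondary objective in 4.2 concerns potential lay users. Section 1.2 describes the device as one for an untrained user, and the intended use in 1.4 is not limited to people at ease with smartphones. If sites follow 6.3 as written, they may turn away people who meet 5.2 but seem less comfortable with a phone. These are plausibly the people most likely to struggle with the app. The word comfortably has no measure, so sites may also apply it differently.

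After enrolment, the plan is silent on whether a subject withdrawn under 9.2 stays in the usability denominator and, if so, with what outcome. Urine collection is both a counted task in 10.6 and a ground for withdrawal in 9.2. If those left out would do no better than those kept, each route can only leave the rate unchanged or raise it.

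Section 8.2 compares failures with a permissible percentage, so a shift of a few points could matter. That percentage is referred to a section 11.6.4, which does not appear in the text available, so no effect on a conclusion can be shown.

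**Working it through.** **The plan's own figure.** The only planning number is at least 250 subjects (10.3). It rests on earlier method comparison studies, a standard and sponsor experience. It has no expected usability rate, precision, alpha or power, so there is no usability calculation to reproduce.

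**The passages side by side.**

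1. *Phone.* 6.3 requires comfort in completing smartphone tasks, while 5.2 requires familiarity. These are different standards, and 6.3 is the stricter. General phone ease is related to success with this app but is not the same thing. Dipping, strip placement and the Color-Board scan are not selected on.
2. *Urine.* The ability to provide a sample appears in 6.3, in the exclusion in 5.3, in 9.2 item 1 and in the task list of 10.6. The overlap is direct, but 5.3 would keep most of it even if 6.3 were deleted.
3. *Denominator.* 10.5 removes subjects with major deviations. It does not say that withdrawal is a deviation, nor that withdrawn subjects are retained. 10.6 lists non-completers under disposition without linking them to the usability result.

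**Scale, under assumptions.** The documents give no pass, withdrawal or screen-out rate. Every input below except the 250 is assumed.

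*(a) Removal after enrolment.* Let N = 250, let r subjects be removed who would all have counted as failures, and let x of the remainder pass (about 95%). The reported rate is x/(N − r); the rate with everyone kept is x/N.

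| r | x/(N − r) | x/N | Difference (points) |
|---|---|---|---|
| 0 | 238/250 = 95.2% | 95.2% | 0 |
| 2 | 236/248 = 95.2% | 94.4% | 0.8 |
| 5 | 233/245 = 95.1% | 93.2% | 1.9 |
| 12 | 226/238 = 95.0% | 90.4% | 4.6 |
| 25 | 214/225 = 95.1% | 85.6% | 9.5 |

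If withdrawn subjects stay in the denominator, the difference is 0 on every row.

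*(b) Selection at entry.* Let s be the share of intended users screened out, p1 the pass rate of those kept and p0 the pass rate of those screened out. The reported rate is p1, the rate in all intended users is (1 − s)p1 + s·p0, and the difference is s(p1 − p0). With p1 = 95%:

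- p0 = 80%: s = 5% gives 0.05 × 15 = 0.75 points; s = 30% gives 0.30 × 15 = 4.5 points.
- p0 = 60%: s = 5% gives 0.05 × 35 = 1.75 points; s = 30% gives 0.30 × 35 = 10.5 points.
- s = 0 or p0 = p1: 0.

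**Yardstick.** The exact (Clopper-Pearson) 95% interval for 238/250 is 91.8% to 97.5%, so it reaches 95.2 − 91.8 = 3.4 points below the estimate. A shift of 4.6 points exceeds that; a shift of 0.8 does not.

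**The case against.** The strongest reply is that 6.3 loosely paraphrases the eligibility criteria. Stage II in 7.1 checks only the inclusion and exclusion criteria, and no test of smartphone tasks at entry is described. A smartphone-based device will mostly be used by people who use smartphones, so part of the point is a limit on generalisability. No section takes withdrawn subjects out of the usability set. If they stay, a subject with no urine would not reach a valid scan and would not pass under 9.1. An insufficient sample may simply mean low volume at a same-day visit and say nothing about the cup or the instructions. Screened subjects are logged (13.2) and withdrawal reasons are recorded (9.2), so selection is at least partly visible.

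All of this stands, and it limits the claim. A reader might infer that the usability percentage is inflated because subjects are selected on the outcome itself. The documents do not support that: phone comfort is a correlate of the outcome, and the loss of withdrawn subjects from the denominator is not stated anywhere. Nor does 9.1 say that a subject completes the study only if urine was tested; it gives that as a sufficient condition.

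The reply leaves three things unanswered. 6.3 and 5.2 still set different standards. No section says how a 9.2 withdrawal counts for usability, or plans to show screen-outs beside the result. And a failed collection is not clearly irrelevant to the device, because 10.7 lists discomfort in using the receptacle as a risk and 8.2 says identified risks will be evaluated in the usability study.

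**Conclusion.** The point holds as a risk of upward bias in a secondary endpoint, not as demonstrated inflation. The difference between 6.3 and 5.2, and the silence on how withdrawn subjects count, are matters of text and need no assumption. The direction rests on one assumption: that people left out would do no better than those kept. The size is unknown. Under the assumed inputs it runs from 0 to about 10 points by either route, and the documents allow zero.

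It would also go too far to call the rate with every insufficient-sample withdrawal scored as a failure the true rate. Some of these may reflect volume alone, and counting them all as device failures could bias the rate downward. That calculation is a bound.

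**What to change.** 1. In 6.3, replace the recruitment sentence with: *Subjects will be recruited according to the criteria in 5.2 and 5.3.* Familiarity with a smartphone then governs entry, and the existing urine-collection exclusion stays.
2. In 10.5 and 10.6, define the usability denominator as all enrolled subjects who were given a kit, and report the rate among completers beside it.
3. Report subjects withdrawn under 9.2 item 1 after receiving a kit by reason: a collection or cup problem, or insufficient volume. State in advance how each reason counts in the main analysis. Add a sensitivity analysis that counts them all as failing the urine-collection task.

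The cost is a few sentences of wording and a finer split of a withdrawal reason that 9.2 already requires to be recorded. The downside is that the reported usability percentage may be slightly lower.
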